6.1.1 Investigational and control drugs

The sponsor will provide the following investigational and control drugs as single-use pre-filled syringes for s.c. injection ([Table 6-1](#)).

Part 1 (Year 1) including “Switch” Day 360:

- Inclisiran sodium 300 mg (equivalent to 284 mg inclisiran) in 1.5 mL solution
- Placebo formulation to this active drug formulation

Placebo will be supplied as sterile normal saline (0.9% sodium chloride in water for injection). Placebo will be administered as a 1.5 mL s.c. injection to match the dose in the inclisiran arm.

The placebo pre-filled syringes will be blinded and look identical to the corresponding inclisiran pre-filled syringes.

Part 2 (Year 2):

- Inclisiran sodium 300 mg (equivalent to 284 mg inclisiran) in 1.5 mL solution

Table 6-1 Investigational and control drug

Investigational/ Control Drug	Pharmaceutical Dosage Form	Route of Administration	Supply Type	Sponsor (global or local)
Inclisiran sodium 300 mg (equivalent to 284 mg inclisiran*) in 1.5 mL solution	Solution for injection	Subcutaneous injection	Solution for injection in pre-filled syringe	Sponsor (global)
Placebo	Solution for injection	Subcutaneous injection	Solution for injection in pre-filled syringe	Sponsor (global)

* Inclisiran is also referred to as KJX839

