6.4 Treatment blinding

Part 1 (Year 1)

Part 1 of the study is randomized, double-blind and placebo-controlled. Participants, investigator staff, persons performing the assessments, and the clinical trial team (CTT) will remain blind to the identity of the treatment from the time of randomization until at least database lock for all Part 1 (Year 1) data, using the following methods: (1) Randomization data are kept strictly confidential until the time of unblinding, and will not be accessible by anyone else involved in the study with the following exceptions: the independent statistician and programmer who need to have access to prepare interim analysis reports for the DMC

[REDACTED]
These personnel will not be involved in any other trial activities. (2) The identity of the treatments will be concealed by the use of study treatment that are all identical in packaging, labeling, schedule of administration, and appearance.

Any [REDACTED] anti-drug antibodies and results from lipid/lipoprotein/PCSK9 measurements after the first administration of study drug until the Day 360 visit should be blinded for participants, investigator staff, persons performing the assessments and the CTT.

Unblinding will occur in the case of participant emergencies and at the conclusion of the study. Unblinding of the CTT and other parties (as needed) will also occur after the Year 1 database lock, which is planned after all participants have completed the Day 360 visit.

Part 2 (Year 2)

Due to the single-arm, open-label design, treatment in Part 2 of the study will be open to participants, investigator staff, persons performing the assessments, and the CTT.

In order to maintain the blind for Part 1 of the study, on the “switch” day (Day 360), participants randomized to placebo in Part 1 will receive blinded inclisiran, while participants randomized to inclisiran in Part 1 will receive blinded placebo.

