6.6 Additional treatment guidance

6.6.1 Treatment compliance

The investigator must promote compliance by informing the participant that compliance is necessary for the participant's safety and the validity of the study. The investigator should also instruct the participant to adhere closely to the scheduled study visits. Study treatment will not be dispensed to the participant but will be administered at designated study visits at the study site by qualified personnel, facilitating compliance. Study drug dosing information should be captured within each designated visit on an appropriate eCRF. The investigator or designee must also maintain an inventory record of study drug (inclisiran/placebo) received and administered.

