1.1 Study design

This study is a two-part (double-blind, placebo-controlled / open-label) multicenter study in adolescents (aged 12 to <18 years) with HoFH and elevated LDL-C (>130 mg/dL / 3.4 mmol/L) on stable, individualized, optimal SoC background lipid-lowering therapy (including maximally tolerated statin treatment). The overall study duration is 748 days.

Following an approximately 4 weeks screening/run-in period, the study has two sequential parts ([Figure 1-1](#)).

- **Part 1 (Year 1):** 12 months double-blind, parallel group period in which participants will be randomized to receive either inclisiran sodium 300 mg (equivalent to 284 mg inclisiran) s.c. or placebo (given at Days 1, 90 and 270).
- **Part 2 (Year 2):** 12 months single arm, open-label follow-up period with all participants receiving inclisiran sodium 300 mg s.c. Participants randomized to placebo in Part 1 will receive inclisiran starting on Day 360 (“Switch” Day 360). Participants randomized to inclisiran in Part 1 will receive placebo on Day 360. This dose of inclisiran/placebo on Day 360 will remain blinded to maintain the blind for Part 1 of the study. All participants will receive subsequent doses of open label inclisiran on Days 450 and 630.

Approximately 12 participants who meet the inclusion/exclusion criteria were to be randomized in a 2:1 ratio to receive either inclisiran sodium 300 mg s.c. or placebo on Day 1 (baseline). Information regarding sample size calculation is provided in [Section 3](#).

Figure 1-1 Study design

* Primary endpoint assessed at Day 330. # "Switch Day": Participants randomized to placebo in Part 1 will start to receive inclisiran on Day 360. Participants randomized to inclisiran in Part 1 will receive placebo on Day 360 only to maintain the blind for Part 1.

The primary endpoint will be measured at Day 330.

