2.1.1 General definitions

Study Day

Study day will be defined as the number of days since the date of first dose of double-blind treatment. The date of first dose of double-blind treatment will be defined as Day 1 and the day before the first dose of study drug will be defined as Day -1.

Therefore, for a particular date, study day will be calculated as follows:

For dates on or after the first date of double-blind treatment,

Study day = Assessment date – Date of first dose of double-blind treatment + 1;

For dates prior to the first date of double-blind treatment,

Study day = Assessment date – Date of first dose of double-blind treatment.

In case, participant has been randomized but has not received double-blind treatment then randomization visit day will be considered as Day 1.

Baseline definition

In general, for both Part 1 and Part 2, baseline value is defined as the last measurement collected on or prior to the first dose of double-blind treatment.

Post-baseline measurement

Post-baseline values are defined as those measurements that were collected after the first dose of double-blind treatment.

When change from baseline is of interest the following formula will be used for each scheduled visit and time-point where baseline and post-baseline values are both available:

Absolute change from baseline = post-baseline value – baseline value.

Percent change from baseline = (post-baseline value – baseline value) / baseline value*100.

LDL-C to be used in analysis

The endpoints involving LDL-C will use the beta quantification (ultracentrifugation) LDL-C for all subjects. In cases where beta quantification (ultracentrifugation) LDL-C values are missing and calculated LDL-C is available, the calculated LDL-C will be used for analysis purposes.

VLDL-C

The endpoints involving VLDL-C will use the beta quantification (ultracentrifugation) VLDL-C for all subjects. In cases where beta quantification (ultracentrifugation) VLDL-C values are missing and calculated VLDL-C is available, the calculated VLDL-C will be used for analysis purposes.

Discontinuation visit mapping

For patients who discontinued the study and come to site for an early exit (EE) visit, the EE visit will be mapped to the next scheduled visit. The mapping details can be found as below:

Table 2-1 Visit mapping

Status	Last attended scheduled visit prior to EE		Mapped visit for EE	
Visit day	Visit name	Visit day	Visit name	Visit day
Discontinued (Early exit)	1	Day 1	90	Day 90

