For occurrence, the presence of at least one SAE / SAE suspected to be related to study treatment / non-SAE has to be checked in a block e.g., among AEs in a ≤ 1 day gap block, if at least one SAE is occurring, then one occurrence is calculated for that SAE.

The number of deaths resulting from SAEs suspected to be related to study treatment and SAEs irrespective of study treatment relationship will be provided by SOC and PT.

These summaries will be provided after full study completion.

Injection site reactions

The number and percentage of participants who reported injection site reaction TEAEs will be summarized in the following ways:

- SOC, PT, treatment group and Part.
- SOC, PT, severity, treatment group and Part.

Listing will be provided for participants with injection site reactions.

The time to the first injection site reaction will also be summarized by treatment and Part using the following categories: $\leq 4h$, $4h$ to $\leq 12h$, $>12h$. The time (hours) to the event will be calculated from the most recent administration of study drug. The duration of the first and the longest injection site reaction will be summarized by treatment and Part using descriptive statistics. The outcome of the first and the longest injection site reaction will be summarized using the following categories: Resolved ($\leq 4h$, $>4h$ to ≤ 7 days, >7 days to ≤ 14 days, >14 days), not resolved and unknown. The total number of injection site reactions per participants will be summarized in categories (e.g., 1, 2, 3, and >3 etc.). Symptoms of injection site reactions will be summarized by treatment group and Part.

Other safety topics

The number and percentage of participants who reported TEAEs of other safety topics will be summarized by PT, treatment group and Part. PTs will be sorted in descending order of frequency in the total column. If a participant reported more than one AE within the same PT, the AE will be counted only once. If a participant reported more than one AE within the same safety topic, the participant will be counted only once at that safety topic. Listings of participants with AEs of other safety topics will be provided.

The Compound Case Retrieval Strategy (CRS) will be used to determine the MedDRA search criteria to be used to identify events of other safety topics.

AEs of other safety topics will include the following:

- Hepatic events
- Renal events
- Hypersensitivity events
- Neurological events
- Psychiatric events

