The time to new-onset diabetes will also be summarized by treatment and Part. Only participants without diabetes at baseline will be included in the analysis. The time (weeks) to new-onset diabetes will be calculated from the date of the first administration of study drug.

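### In the Part 2 placebo-inclisiran column, time to new-onset diabetes counts from the first saline injection, about 51 weeks before first inclisiran

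*SAP*

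**What the plan says.** SAP 2.7.4 (Diabetes assessment) states "The time to new-onset diabetes will also be summarized by treatment and Part", limits the analysis to participants without diabetes at baseline, and then fixes the origin: "The time (weeks) to new-onset diabetes will be calculated from the date of the first administration of study drug". It gives no separate origin for Part 2 or for either treatment sequence.

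Three other places bear on how this is read:

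- **What counts as study drug.** Protocol 6.6.1 refers to an "inventory record of study drug (inclisiran/placebo) received and administered", so placebo is included. Protocol 6.1.1 says that the placebo is normal saline.
- **When the first administration falls.** SAP 2.1.1 sets Day 1 at the first double-blind dose and adds that "the day before the first dose of study drug will be defined as Day -1", so it treats the two as the same event. Protocol 6.4 uses the same phrase for the start of the blinded interval: results "after the first administration of study drug until the Day 360 visit should be blinded".
- **When the placebo arm first receives inclisiran.** SAP 1.1: "Participants randomized to placebo in Part 1 will receive inclisiran starting on Day 360". The inclisiran arm receives placebo on that day.

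SAP 2.1 reports Part 2 in two columns, inclisiran-inclisiran and placebo-inclisiran, with a total where the table shells call for one.

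**The concern.** Time to onset is normally read as latency: how long after exposure began did the event appear? In Part 1 the stated origin serves that purpose in both columns, because each arm starts its assigned treatment on Day 1. In Part 2 it serves that purpose only for inclisiran-inclisiran. For placebo-inclisiran, the value adds the placebo year to the time on inclisiran.

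The placebo-inclisiran participants are the only ones whose first months on inclisiran fall in Part 2. New-onset diabetes is also one of the topics that Protocol 10.2.3 names for regular DMC review. With so few participants, one case could be the whole content of the column, so the latency printed for it should mean what a reader takes it to mean.

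**Working it through.** The documents give no figure for this point, so there is nothing to reproduce. The check is date arithmetic on the nominal schedule.

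**Inputs.** First study injection: Day 1 (SAP 2.1.1). First inclisiran in the placebo arm: Day 360 (SAP 1.1). Part 2 runs from after Day 360 dosing (SAP 2.1) to the Day 720 visit (Protocol Table 8-1). Fasting glucose and HbA1c belong to both chemistry panels (Protocol Table 8-3). One or other panel is drawn on Days 450, 510, 630 and 720. The Day 360 sample precedes the injection (Protocol 6.7.2), so Day 450 is the first scheduled Part 2 measurement.

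**Offset.** (360 - 1)/7 = 359/7 = 51.3 weeks.

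**Times for a Part 2 placebo-inclisiran case, by visit of detection:**

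| Visit | SAP origin, (day - 1)/7 | From first inclisiran, (day - 360)/7 |
|---|---|---|
| Day 450 | 64.1 weeks | 12.9 weeks |
| Day 510 | 72.7 weeks | 21.4 weeks |
| Day 630 | 89.9 weeks | 38.6 weeks |
| Day 720 | 102.7 weeks | 51.4 weeks |

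**Comparison within Part 2.** Two participants detected on Day 450, one in each column, both read 64.1 weeks. One is 64.1 weeks from first inclisiran, the other 12.9.

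**Comparison across Parts.** An inclisiran participant detected on Day 90 in Part 1 reads (90 - 1)/7 = 12.7 weeks. A placebo-inclisiran participant detected on Day 450 has nearly the same time since first inclisiran (12.9 weeks) but reads 64.1.

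**Sensitivity to the actual dosing date.** If Day 360 dosing is up to two weeks early or late (an assumption), the offset is (359 - 14)/7 = 49.3 to (359 + 14)/7 = 53.3 weeks. If that dose is missed and first inclisiran is given on Day 450, it is 449/7 = 64.1 weeks.

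**Alternative reading.** Because the summary is split by Part, the origin might be taken as the first administration within that Part. The SAP does not say so, and the usage above points to Day 1. Under that reading placebo-inclisiran would be timed correctly, but inclisiran-inclisiran would be timed from its Day 360 placebo injection. Neither single origin gives time since first inclisiran in both columns.

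**Number affected.** About 12 participants at 2:1 gives 12 × 1/3 = 4 on placebo.

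**The case against.** The strongest reply is that nothing is miscalculated. The SAP defines time since first study injection, and that agrees with its general Day 1 baseline for both Parts and with an at-risk group fixed before treatment starts. This stands. A reader might infer that these onset times are simply wrong or reported late; the documents do not support that, because the values are right for the stated quantity and fall short only as latency from inclisiran.

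A second inference would be that the floor of about 51 weeks is a distortion peculiar to placebo-inclisiran. It is not: with a Day 1 origin, every Part 2 event in either column comes after about 51 weeks. What differs is that for inclisiran-inclisiran the figure is also time since first inclisiran.

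A third would be that the rule conceals an early-onset pattern. That goes too far. The column is reported separately, adverse events are listed (SAP 2.7.1), and laboratory data are listed by participant and visit (SAP 2.7.3). For about 4 participants a reader can recover the interval. Scheduled laboratory data could not show a Part 2 onset before Day 450 under either origin.

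The rule for injection site reactions, "The time (hours) to the event will be calculated from the most recent administration of study drug", shows that the SAP can choose an origin to suit the event. It is no precedent for using first inclisiran: it concerns a local reaction timed in hours, and it counts saline injections too.

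Finally, moving the origin alone would create a new problem. SAP 2.7.4 sets at-risk status only at the Day 1 baseline and does not remove from Part 2 someone who became diabetic in Part 1. A placebo participant whose HbA1c first reached 6.5% in Part 1 and was still there on Day 450 could then appear as onset 12.9 weeks after first inclisiran. This objection stands, and the fix has to deal with it.

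**Conclusion.** The point holds as one of interpretation and labelling. As written, Part 2 placebo-inclisiran times exceed time since first inclisiran by 51.3 weeks on the nominal schedule, so that column does not show latency from inclisiran and is not on the same exposure scale as inclisiran-inclisiran. The SAP specifies no summary of time since first inclisiran for that group.

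The practical weight is small. The summary is descriptive, concerns about 4 participants, and matters only if a case occurs. Protocol 1.1 reports no difference from placebo in new or worsening diabetes in the adult programme, so there may be none. Case counts, assignment of events to Parts and the primary endpoint do not change. The conclusion assumes that first administration means Day 1, as usage elsewhere in both documents indicates, and that Day 360 dosing is on schedule. A total column would combine the two scales, but the table shells that decide whether one appears are not available here.

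**What to change.** Amend the timing sentence in SAP 2.7.4 for the Part 2 summary:

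1. Calculate time from the actual date of first inclisiran administration in each group. This is Day 1 for inclisiran-inclisiran. For placebo-inclisiran it is the Day 360 dose or, if that was not given, the first inclisiran dose actually received.
2. Label the result *time since first inclisiran dose*, including in any total column.
3. Include only participants who had not already met the new-onset diabetes definition before Day 360 dosing, in addition to the existing requirement of no diabetes at baseline.
4. If wanted, keep time since first study injection in the listing under its own label.

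The cost is one added Part 2 at-risk condition and one derivation line. Injection dates are already collected, so no new data are needed. The two Part 2 columns will then cover different ranges (about 51.3 to 102.7 weeks and 0 to 51.4 weeks). That reflects the real difference in exposure and should be footnoted.

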2.7.5 Vital signs

Absolute values and change from baseline will be summarized for vital sign parameters by visit, time-point, treatment group and Part. For SBP and DBP, average of 3 readings will be used for analysis while all 3 readings will be provided in the listing. Baseline and change from baseline in height, weight, and BMI will be assessed with/without using age- and sex-adjusted z-scores and summarized by visit, treatment group and Part.

The number and percentage of patients meeting clinically notable criteria at any time, considering all data collected after first dose of double-blind treatment, from scheduled, unscheduled and premature discontinuation visits will be summarized by treatment group and Part. The worst post-baseline value in each part will be used for this analysis. Notable criteria are defined in [Appendix 5.6](#). Clinically notable criteria will be met when both of the following occur:

- Post-baseline value meets the clinically notable criteria.
- Baseline value does not meet the clinically notable criteria.

The baseline value is the last value prior to and up to Day 1 of the double-blind treatment.

All vital signs data will be listed by treatment group, participant, and visit/time and if clinically notable criteria are met, abnormalities will be flagged.

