6.7.2 Instruction for prescribing and taking study treatment

Investigational and control drugs will not be dispensed to the participants. Study drug injections will be performed exclusively at the study site by qualified clinical study site staff under the supervision of the investigator or designee.

The site of injection is the abdomen, alternating sides for each injection. Injections should not be done into areas of active skin disease or injury such as sunburns, skin rashes, inflammation, tattoos or skin infections.

Participants will be administered one s.c. injection of study drug at pre-defined visits as specified in the Assessment Schedule ([Table 8-1](#)) and summarized below.

- **Part 1:** Each participant will receive one injection of blinded inclisiran or placebo on Day 1, a second injection of blinded inclisiran or placebo on Day 90 and a subsequent injection of blinded inclisiran or placebo on Day 270 (“6 months dosing”).
- **Part 2:** Participants randomized to placebo in Part 1 will receive a single injection of blinded inclisiran on Day 360, while participants randomized to inclisiran in Part 1 will receive a single injection of blinded placebo on Day 360. All participants will receive subsequent doses of open-label inclisiran on Day 450 and Day 630.

Injections will be administered after all other study assessments have been completed for the visit. At the Randomization (Day 1) and Day 360 visits, vital signs (blood pressure and pulse) and ADA (Day 1 only) will be assessed a second time 4 hours after injection

Participants must be observed in the clinic for at least 4 hours post injection on Day 1 and Day 360 (i.e. first dosing of inclisiran) and for at least 30 minutes post injection for all other dosing visits before being discharged.

Should a participant develop signs or symptoms of anaphylaxis when study drug is injected, the investigator will need to collect a blood sample for tryptase within 30 minutes of the onset of anaphylaxis (or as soon as possible).

All kits of study treatment assigned by the IRT will be recorded in the IRT system.

All injections to the participant as well as study drug interruptions/discontinuations (i.e. no injection at a designated dosing visit) during the study must be recorded on an appropriate eCRF.

7 Informed consent procedures

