2.7 Safety analyses

In general, for Part 1 safety analyses, the SAF will be used; for Part 2 safety analysis, the OAS will be used.

Safety summaries will include only treatment emergent adverse events (TEAEs) by Part. For Part 1, TEAEs are adverse events (AEs) that started on or after the first dose of double-blind treatment or adverse events (AEs) that were present prior to start of double-blind treatment but increased in severity in Part 1. For Part 2, TEAEs are defined as AEs starting after the Day 360 dosing time or AEs that were present prior to the Day 360 dosing time but increased in severity in Part 2. For Part 1, if the AE start date is the same as the date of the first dose of double-blind treatment but the time is not available for comparison, the AE will be considered as treatment emergent; for Part 2, if the AE start date is the same as the date of the Day 360 treatment but the time is not available for comparison, the AE will be considered as treatment emergent

Vital signs values that have complete data and time values will be assigned to pre- or post-dose assessment (as per protocol) based on the actual date/time. For values with missing date/time, the scheduled visit date and time will be used. This rule will be applied to data from scheduled visits only. If a measurement scheduled as pre-dose is actually performed post-dose, or vice versa, the data will not be used for by visit/time point summary.

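### The SAP 2.7.5 vital-sign baseline is set by day, not by dose, and read literally can select the 4-hour post-injection reading on Day 1

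*SAP*

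**What the plan says.** SAP 2.7.5 (Vital signs) defines its own baseline: "The baseline value is the last value prior to and up to Day 1 of the double-blind treatment". SAP 2.1.1 fixes what Day 1 is: "The date of first dose of double-blind treatment will be defined as Day 1".

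Protocol 6.7.2 requires injections to follow all other assessments at a visit. It then adds, for the Day 1 and Day 360 visits, that "vital signs (blood pressure and pulse) and ADA (Day 1 only) will be assessed a second time 4 hours after injection". Day 1 therefore has one blood pressure and pulse assessment before the injection and one after it.

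Other SAP text is tied to the dose:

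- SAP 2.1.1, in a sentence that begins by saying it applies in general and to both Parts, states that the "baseline value is defined as the last measurement collected on or prior to the first dose of double-blind treatment".
- The definition that follows it in SAP 2.1.1 carries no such qualifier: "Post-baseline values are defined as those measurements that were collected after the first dose of double-blind treatment".
- SAP 2.7 says that vital signs with a complete date and time "will be assigned to pre- or post-dose assessment (as per protocol) based on the actual date/time".
- SAP 2.7.3 defines the laboratory baseline as the last value before the first double-blind dose.

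SAP 2.7.5 counts a participant as having a notable value only if a post-baseline value meets the criterion and the baseline value does not. On the data for that count it reads: "considering all data collected after first dose of double-blind treatment, from scheduled, unscheduled and premature discontinuation visits will be summarized by treatment group and Part".

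**The concern.** The vital-sign sentence is the only one of these rules that stops at a calendar day. A reading taken 4 hours after the injection normally carries the Day 1 date, so it is the last value up to Day 1. Because the general definition in SAP 2.1.1 is qualified, a programmer could treat SAP 2.7.5 as a deliberate exception and select by date.

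The 4-hour reading is the scheduled check for an acute change in blood pressure or pulse after the first injection. Taken as baseline, it is compared with itself. A participant with a notable 4-hour value would also fail the second half of the two-part test and could not be counted for that criterion. SAP 2.1.1 uses one baseline for both Parts, so the shift would extend to Part 2. That includes the 4-hour reading on Day 360, which for participants first randomized to placebo follows their first inclisiran dose.

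**Working it through.** The plan gives no figure on this point, so there is nothing to reproduce. The check has two steps: classify the Day 1 4-hour reading under each rule, then follow one illustrative participant through both baselines.

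**Step 1. How each rule treats the Day 1 4-hour blood pressure or pulse**

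| Rule | Anchor | 4-hour reading is |
|---|---|---|
| SAP 2.7.5, baseline sentence | Day 1 | eligible as baseline, and the last eligible value |
| SAP 2.1.1, baseline | first dose | not baseline |
| SAP 2.1.1, post-baseline | first dose | post-baseline |
| SAP 2.7, pre-/post-dose assignment | actual date and time | post-dose |
| SAP 2.7.5, data for the notable count | first dose | included as data after the first dose |

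Read by date, the baseline sentence makes one value both baseline and post-baseline, and it conflicts with another sentence in its own section.

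**Step 2. Consequence for one participant**

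Inputs: the systolic values are assumed for illustration and are not trial data. They are screening 112, Day 1 pre-dose 110, Day 1 at 4 hours 85, Day 30 108 and Day 90 109 mmHg. The notable limits, below 90 or above 145 mmHg, come from SAP Table 5-3. Change is the post-baseline value minus baseline (SAP 2.1.1).

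| | Date-only reading of 2.7.5 | SAP 2.1.1 rule |
|---|---|---|
| Baseline | 85 (4-hour reading) | 110 (pre-dose) |
| Change at 4 hours | 85 - 85 = 0 | 85 - 110 = -25 |
| Change at Day 30 | 108 - 85 = +23 | 108 - 110 = -2 |
| Change at Day 90 | 109 - 85 = +24 | 109 - 110 = -1 |
| Is baseline notable (below 90)? | yes | no |
| Low value counted as notable? | no | yes |

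The 4-hour change is zero under the date-only reading whatever the values are. Later changes are shifted by the pre-dose value minus the 4-hour value, here 110 - 85 = +25.

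**Step 3. Weight of one lost event**

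About 12 participants randomized 2:1 gives about 8 on inclisiran and 4 on placebo. One participant missing from the notable count is 1/8 = 12.5% of the inclisiran arm or 1/4 = 25% of the placebo arm.

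**The case against.** The strongest reply is that the SAP, read as a whole, already places the 4-hour reading after baseline. The post-baseline definition in SAP 2.1.1 is unqualified. SAP 2.7 labels the reading post-dose by its clock time, and SAP 2.7.5 itself draws notable values from data after the first dose. On this view the disputed sentence is loose shorthand for the general rule. Where the SAP clearly means to depart from that rule it spells out the derivation, as in SAP 2.7.4 for fasting glucose, where Screening and Day 1 are averaged.

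Most of this stands, and it rules out three stronger readings that a reader might infer:

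- *That the plan settles on the 4-hour reading because the specific sentence overrides the general one.* Neither document states such a precedence. What the text shows is a contradiction.
- *That a first-dose change would be hidden.* SAP 2.7.5 summarizes absolute values by visit and time-point and lists every reading, so a 4-hour value of 85 would still appear in both.
- *That all 12 baselines are wrong.* That follows only if the baseline is programmed by date alone and each participant has the 4-hour reading.

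The reply does not remove the defect. The sentence as written gives a different answer from the definitions around it. The pre-/post-dose rule in SAP 2.7 classifies readings but does not define baseline.

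**Conclusion.** The point holds as an internal contradiction in the SAP with a definite consequence if the sentence is applied by date. The Day 1 4-hour change would be zero, later changes in both Parts would be shifted, and a notable 4-hour value would be left out of the notable-value count. The flag in the listing could also be lost if it is programmed on the same two-part test, which SAP 2.7.5 leaves open.

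The reach is limited to blood pressure and pulse outputs that depend on baseline. Height, weight and BMI have no 4-hour repeat under Protocol 6.7.2, and the primary endpoint is not involved. The size in any participant depends on the actual 4-hour change, for which the documents give no data; the -25 mmHg above is only an illustration. The conclusion assumes that the 4-hour reading is dated Day 1 and that the programmer follows the SAP 2.7.5 sentence and not SAP 2.1.1. It is a minor correction, worth making because the sentence concerns a measurement deliberately repeated after dosing.

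**What to change.** In SAP 2.7.5, replace the baseline sentence with the one SAP 2.7.3 already uses for laboratory data, so that the vital-sign baseline is the last value before the first dose of double-blind treatment. Add one sentence stating that the Day 1 4-hour blood pressure and pulse readings are post-baseline. If vital-sign datasets have already been programmed, check that the baseline flag uses the dose time and not the visit date.

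The cost is two sentences and one programming check. No new data are needed and no other analysis changes.
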